Study Title “IVIg for Small Fiber Neuropathy With Autoantibodies to TS-
HDS and FGFR3”

NCT number: NCT03401073

Document Date: 11/29/2022

Protocol:

Study Design: This was a prospective 6-month double-blind placebo-controlled pilot study of IVIG for treatment of suspected immune mediated SFN associated with TS-HDS or FGFR-3. The trial was registered with ClinicalTrials.gov (NCT03401073).

Subjects: Potential research subjects were recruited from the panel of patients seen by neuromuscular/peripheral nerve groups at Beth Israel Deaconess Medical Center (BIDMC) (Boston, MA) and HonorHealth Neurology (Phoenix, AZ) and by patients seen at neighboring institutions in the Boston and Phoenix areas. Additional referrals were obtained through ClinicalTrials.gov. All recruited subjects provided signed informed consent as approved by the Institutional Review Boards of BIDMC and HonorHealth.

Inclusion Criteria: Patients were potentially eligible if they had clinically evident SFN in a length dependent or non-length dependent pattern as confirmed by history of symptoms that included burning, shooting, or prickling pain or dysesthesia for at least 6 months and examination findings demonstrating loss of pain sensation and/or loss of temperature detection in the distribution of pain. Subjects also required evidence of reduced intra-epidermal nerve fiber density (IENFD) seen on skin biopsy in the region corresponding to examination abnormalities, based on age and sex-matched normative values, using PGP 9.5 as the immunostain.¹⁵ Subjects required a baseline daily pain score on a visual analogue scale (VAS) of greater than or equal to 4/10. Patients also required elevated titers of autoantibodies to TS-HDS or FGFR-3 as measured by the Neuromuscular Clinical Laboratory at Washington University in St Louis using standard enzyme linked immunoassay (ELISA) assays as previously published.^{14,16} Antibody titers were measured at the time of screening and abnormal values measured at the Washington University laboratory within the 6 months prior to screening were accepted. Normative values are <10,000 for TS-HDS and <3,000 for FGFR3.

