Primary Outcome: The primary efficacy endpoint for this study was the change in IENFD between visits 1 and 8. We defined a clinically relevant change in disease endpoint as a >2.0 fiber/millimeter increase in IENFD between screening and final visit. We anticipated no change in IENFD between visits 1 and 8 in the placebo treatment arm. The change in IENFD was based on prior studies of lifestyle modification in diabetic neuropathy where increases in IENFD of >2 fibers/mm over 1 year were seen in 25% of patients associated with an improvement in neuropathic pain.²² Pain was not selected as a primary outcome measure because a separate ongoing clinical trial using IVIG in small fiber neuropathy was already investigating pain as an endpoint,² and also because of our specific interest was in evaluating IVIG for potential impact on disease modification.

Secondary Outcomes: Two secondary outcome measures are included in this study:

- 1) The change in neuropathic pain severity between visits 1 and 8.

We expected that individuals with immune mediated small fiber neuropathy treated with IVIG would have a >2-point reduction in neuropathic pain VAS score between screening and final visit. We anticipated a <1.5-point reduction in neuropathic pain VAS score between screening and final visit in the placebo group.

- 2) The change in quantified UENS scores, between screening and final visit.

We expected that individuals with immune mediated SFN treated with IVIG would have a >1 point reduction in the UENS score between screening and final visit. We expected that the placebo treated group would have no change in UENS score between screening and final visits.

Exploratory Outcomes: Safety in response to IVIG infusion and changes in distribution or character of pain associated with SFN in patients treated with IVIG.

This pilot study was being conducted in order to obtain adequate preliminary data for a larger clinical trial but was powered to answer the primary endpoint analysis. Secondary endpoints and exploratory endpoints are not included in the power analysis. The sample size of 10 participants per group was determined with an assumed change in IENFD rate of 0 fibers/millimeter in the placebo group and >2.0 fibers/millimeter in the IVIG group, a 1-sided α of 5%, and 80% power between the 2 groups, including the assumption of a dropout rate of 10% (2 patients). Therefore, the aim was to include in total 20 patients in the study.

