The results were analyzed according to the intention-to-treat (ITT) protocol. For the primary ITT analysis, missing values were imputed as no change from baseline. Participants were analyzed for efficacy according to randomized treatment. For the SF-36 Health Survey, biopsy results, and UENS examination findings, the difference between baseline (screening period) and the end of the final visit was calculated. For the primary outcome measure, the proportion of patients with a decrease of at least 2.0 fibers/millimeter was compared between the IVIG and placebo groups with a χ^2 test, with mean and standard deviations reported. For secondary outcome measure, mean change in values between groups was compared using a student's T-test (2 tailed, 2 sample, homoscedastic variance). For pain VAS scores, ANOVA was used to measure differences in pain scores between IVIG and placebo groups.

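### The primary test counts patients who lose at least 2.0 fibers/mm, although the plan defines benefit as a gain of more than 2.0

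*Combined protocol and SAP*

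**What the plan says.** All of this is current text in the combined protocol and SAP.

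- **Entry (Inclusion Criteria).** Patients need "evidence of reduced intra-epidermal nerve fiber density (IENFD) seen on skin biopsy", so low density is the abnormality and further loss is worsening.
- **Definition of benefit (Primary Outcome).** "We defined a clinically relevant change in disease endpoint as a >2.0 fiber/millimeter increase in IENFD between screening and final visit".
- **Basis for the threshold (Primary Outcome).** Earlier lifestyle studies in which "increases in IENFD of >2 fibers/mm over 1 year were seen in 25% of patients".
- **Placebo expectation (Primary Outcome).** "We anticipated no change in IENFD between visits 1 and 8 in the placebo treatment arm".
- **Sample size (paragraph after Exploratory Outcomes).** Ten per group, from an "assumed change in IENFD rate of 0 fibers/millimeter in the placebo group and >2.0 fibers/millimeter in the IVIG group", one-sided 5% alpha, 80% power and 10% dropout.
- **Primary test (final paragraph).** "the proportion of patients with a decrease of at least 2.0 fibers/millimeter was compared between the IVIG and placebo groups", by chi-square, "with mean and standard deviations reported".
- **Missing data (final paragraph).** "For the primary ITT analysis, missing values were imputed as no change from baseline".

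The final paragraph contains the only sentence that states the primary test. No section defines an endpoint based on nerve loss.

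**The concern.** The sentence that decides the primary result contradicts the benefit it should test, in two ways.

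1. **Direction.** The outcome definition counts gains; the test counts losses.
2. **Cut-off.** The definition excludes a change of exactly 2.0; the test includes it.

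If losses really were counted, a patient who regrew more than 2.0 fibers/mm and a patient who did not change fall in the same cell of the table. Regrowth would show only in the descriptive means and SDs. The test could then favour IVIG only through nerve loss on placebo, where the plan expects no change.

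If *decrease* is merely the wrong word, a reader still cannot tell from the document which direction and cut-off produced the reported result. The plan says the trial was powered for this endpoint and is meant to supply preliminary data for a larger one, so this rule needs to be unambiguous.

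**Working it through.** **1. The two rules side by side**

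| Change in IENFD (fibers/mm) | Primary Outcome definition | Primary test as written |
|---|---|---|
| Gain above 2.0 | counted | not counted |
| Gain of exactly 2.0 | not counted | not counted (counted if only the direction is corrected) |
| Between −2.0 and +2.0 | not counted | not counted |
| Loss of 2.0 or more | not counted | counted |
| Missing (set to no change) | not counted | not counted |

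No patient can be counted under both rules.

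**2. The plan's own figure.** The dropout step reproduces: 9/(1 − 0.10) = 10 per arm, 18/0.90 = 20 in total. The 9 per arm cannot be reproduced, because neither an SD nor responder rates are given.

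**3. Consequence that needs no SD.** With *a* and *b* patients counted among 10 IVIG and 10 placebo, the uncorrected statistic is

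χ² = 20 × [a(10 − b) − b(10 − a)]² / [10 × 10 × (a + b) × (20 − a − b)].

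Suppose all 10 IVIG patients gain more than 2.0 and no placebo patient changes by 2.0 in either direction.

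- Primary Outcome definition: a = 10, b = 0. χ² = 20 × 100² / (100 × 10 × 10) = 20.0, two-sided p = 0.000008.
- Test as written: a = 0, b = 0. The denominator is zero and no statistic exists.

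The two-sided test also does not distinguish benefit from harm by itself: 0/10 IVIG versus 4/10 placebo and 4/10 versus 0/10 both give χ² = 20 × 40² / (100 × 4 × 16) = 5.0, p = 0.025.

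**4. Cut-off, with direction corrected.** Suppose one IVIG patient has a gain of exactly 2.0.

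- Not counted, 3/10 versus 0/10: χ² = 20 × 30² / (100 × 3 × 17) = 3.53, two-sided p = 0.060.
- Counted, 4/10 versus 0/10: χ² = 5.0, two-sided p = 0.025.

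This crossing of 0.05 holds for the two-sided uncorrected test. At one-sided 5%, 3/10 versus 0/10 is already significant (p = 0.030), and the crossing comes one patient earlier: 2/10 versus 0/10 has χ² = 20 × 20² / (100 × 2 × 18) = 2.22, one-sided p = 0.068.

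**5. Illustration under an assumed SD.** Assume normal changes with means 0 (placebo) and 2.0 (IVIG) and a common SD of 1.63. That SD is back-solved: it gives 80% power for a one-sided 5% t-test with 9 per arm and a difference of 2.0. The plan does not specify a t-test for this outcome.

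- Placebo: P(loss of 2.0 or more) = Φ(−2.0/1.63) = 0.110.
- IVIG: Φ((−2.0 − 2.0)/1.63) = 0.0071.

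The chance that the test as written is significant in favour of IVIG follows by summing binomial probabilities over all 2x2 tables, with 10 per arm in the denominator. The lower end of each range has 9 observed and 1 imputed per arm; the upper end has 10 observed.

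| Assumed SD | Two-sided 5% | One-sided 5% |
|---|---|---|
| 1.25 | 0.1% | 1.1–1.5% |
| 1.63 | 1.1–1.7% | 6.3–8.2% |
| 3.0 | 7.6–9.7% | 19–22% |

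At SD 1.63 the chance that nobody in either arm loses 2.0 or more, leaving no statistic, is 29–33%. With the direction corrected and the same means, responder rates are 0.50 versus 0.110 and power is 38–44% two-sided or 57–63% one-sided.

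**The case against.** The strongest reply is that this is one wrong word. Every other directional statement about IENFD is a gain, patients enter with reduced density, and no worsening endpoint exists. Both secondary outcomes, pain and UENS, improve by going down, which is a plausible source of the slip. I accept that this is the likeliest explanation. It does not settle the matter: the sentence is in the past tense, and a document written after a wrongly coded analysis would read the same. The changed cut-off also means the sentence is not simply the Primary Outcome rule with one word swapped.

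Other points stand in part.

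- **The cut-off is minor.** It matters only if a change equals exactly 2.0, and the plan gives no data or reporting precision to show that this occurred. Alone it would not demand correction. The 3-to-4 example also depends on the test: with Yates correction 4/10 versus 0/10 gives p = 0.094, and two-sided Fisher gives 0.087.
- **The SD is assumed.** The power figures are illustration only; the conflict is established without them.
- **A rewrite could misdescribe history.** If losses, or at least 2.0, were actually used, silently changing the sentence would hide that. The correction must therefore follow a check of what was coded.
- **Regrowth is still reported.** Means and SDs would show it, but they are not the primary test.

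**Conclusion.** The conflict holds and must be fixed. As written, the primary decision rule counts worsening, while the definition, rationale and sample-size assumption all concern regrowth. In the plan's best case the written rule yields no test at all, where the intended rule gives p = 0.000008; this rests on no assumption about variability. If losses were literally counted, the chance of a significant result favouring IVIG would be 1.1–1.7% two-sided or 6.3–8.2% one-sided at an assumed SD of 1.63, and 0.1–9.7% or 1.1–22% over SDs from 1.25 to 3.0.

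Confidence is high that the text contradicts itself. It does not extend to a claim that losses were counted, which the document cannot show. Correcting the direction does not by itself deliver the stated 80% power; that is a separate issue.

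**What to change.** 1. Check the analysis code or dataset for the direction and cut-off used in the primary comparison.
2. Align the primary-test sentence with the Primary Outcome paragraph, so that it specifies an increase of more than 2.0 fibers/mm from screening to the final visit, and state which count was actually analysed. If *decrease* was only a slip, this is a plain correction. If another rule was coded, keep a record of it beside the corrected definition.
3. If losses were counted, or if at least 2.0 was used and any patient's change was exactly 2.0, rerun the 2x2 comparison under the Primary Outcome definition. Keep the existing no-change imputation, so that a missing biopsy remains a non-responder in the randomised denominator. Label the rerun as a re-analysis and report both results.

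**Cost:** a check of code or data, one sentence of wording, and at most one rerun on existing biopsy data. No new patients or procedures.

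### The primary χ² test is under-specified for 10 patients per arm: expected responder cells are about 1 to 3, and the corrected and uncorrected versions reach different verdicts at the plan's own level

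*Combined protocol and SAP*

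**What the plan says.** The final paragraph of the Statistical Analysis Plan reduces the primary outcome to a responder proportion, which "was compared between the IVIG and placebo groups with a χ^2 test". It names no continuity correction, exact alternative or small-count rule, and does not give the sidedness of this test. Missing values are imputed as no change, so a patient who drops out stays in the analysis as a non-responder.

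The sample-size paragraph states: "The sample size of 10 participants per group was determined", with "a 1-sided α of 5%, and 80% power between the 2 groups". It also says that the trial, although a pilot, was powered for its primary endpoint. The effect is given as an "assumed change in IENFD rate of 0 fibers/millimeter in the placebo group and >2.0 fibers/millimeter in the IVIG group". No standard deviation and no responder rate per arm is given.

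The only responder rate in the document is under Primary Outcome, from lifestyle modification in diabetic neuropathy: "increases in IENFD of >2 fibers/mm over 1 year were seen in 25% of patients". For placebo: "We anticipated no change in IENFD between visits 1 and 8 in the placebo treatment arm".

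**The concern.** The χ² p-value is a large-sample approximation. It is usually trusted when every expected cell count is at least 5, and two arms of 10 with few responders fall well short of that. Two things follow. The nominal 5% is not guaranteed to be the real error rate. And the name of the test no longer fixes the answer: with cells this small, the continuity correction, which some software applies by default, moves the p-value by a factor of about three.

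This is the trial's primary p-value. If the choice between versions is open when the data are seen, the success criterion has not been fully fixed in advance.

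**Working it through.** **Inputs.** n = 10 per arm, 1-sided α = 5% and a dropout allowance of 10% come from the sample-size paragraph. The 25% comes from the cited precedent. The placebo rate of about 0% is my reading of the no-change assumption. The rates 50% for IVIG and 5% for placebo are mine, to show a range. A responder is taken to be a patient whose IENFD *increases* past the cut, as under Primary Outcome. The analysis paragraph words the direction differently, which is a separate matter.

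**The plan's own figure.** The 20 cannot be reproduced, because neither a standard deviation nor a pair of responder rates is given. The dropout step is consistent: 18/0.9 = 20. For a difference in means of 2.0, 9 to 10 per arm implies a standard deviation of about 1.7 to 1.8. For responders against 0%, it implies an IVIG rate of about 44% to 47%.

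**Expected responder cells.** With equal arms, each is half the total number of responders.
- 10% in both arms: 10 × 0.10 = 1.0
- 25% vs 0%: 10 × 0.125 = 1.25
- 50% vs 0%: 10 × 0.25 = 2.5
- 50% vs 12%: 10 × 0.31 = 3.1

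Reaching 5 needs at least 10 responders among 20 patients. At 50% vs 0% that has probability 0.5^10 = 0.1%. At 25% vs 0% the chance of no responder at all is 0.75^10 = 5.6%, and the statistic is then 0/0.

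**One table in full: 3/10 vs 0/10.** The pooled rate is 3/20 = 0.15, and the standard error is √(0.15 × 0.85 × 2/10) = 0.1597.
- Uncorrected: z = 0.30/0.1597 = 1.879, one-sided p = 0.030 (two-sided 0.060).
- Corrected: subtract ½(1/10 + 1/10) = 0.1 from the difference; z = 0.20/0.1597 = 1.252, one-sided p = 0.105.

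Similar splits occur at 5/10 vs 1/10 (0.026 vs 0.072) and 6/10 vs 2/10 (0.034 vs 0.085).

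**True size.** For each test I took every 10-vs-10 table significant at one-sided 5%, summed the binomial probabilities at a common response rate, and maximised over that rate.
- Uncorrected χ²: 0.7% at a rate of 5%, 2.5% at 10%, 4.8% at 25%, 5.0% at 30%, and a maximum of 5.8% at 50%. It exceeds 5% only between about 30% and 70%.
- Corrected χ²: maximum 2.1%.

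**Power.** With no placebo responders, the uncorrected test needs at least 3/10 on IVIG and the corrected test at least 4/10.
- At 25%: P(Bin(10, 0.25) ≥ 3) = 47.4%; P(≥ 4) = 22.4%.
- At 50%: P(Bin(10, 0.5) ≥ 3) = 94.5%; P(≥ 4) = 82.8%.

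**Exact alternatives at one-sided 5%, arms as the fixed margins.** Barnard's p-value is the largest probability, over the common response rate, of all tables whose pooled z is at least the one observed. Boschloo's test does the same with tables ordered by Fisher's p-value.

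| Test | Max size | p, 3/10 vs 0/10 | Power 25% vs 0% | 50% vs 0% | 50% vs 5% |
|---|---|---|---|---|---|
| χ², uncorrected | 5.8% | 0.030 | 47.4% | 94.5% | 79.2% |
| χ², corrected | 2.1% | 0.105 | 22.4% | 82.8% | 62.8% |
| Fisher | 2.1% | 0.105 | 22.4% | 82.8% | 62.8% |
| Boschloo | 4.5% | 0.058 | 22.4% | 82.8% | 72.1% |
| Barnard, pooled score | 4.7% | 0.044 | 47.4% | 94.5% | 79.1% |

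Comparing all tables, Barnard's test and the uncorrected χ² differ at one only: 7/10 vs 3/10 (0.058 against 0.037).

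**The case against.** The best defence is that the harm to the error rate is marginal. The excess is at most 0.8 points and needs a common response rate of about 30% or more. If placebo patients hardly change, as the plan expects, the null lies where the uncorrected test is conservative. That stands. A reader might infer from the small cells that the type I error is inflated in general; the plan's own assumptions point the other way. Nor can the claim be carried over to a two-sided test, whose maximum size with 10 per arm is 4.2%. Arguing from smaller arms after dropout does not fit either, because the imputation rule keeps dropouts in the analysis.

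Several further points are fair. The 25% comes from another disease over one year, and the plan does not assume it for IVIG. A clear result is safe: 4/10 vs 0/10 is significant at one-sided 5% by the uncorrected (0.013), corrected (0.047), Fisher (0.043) and Boschloo (0.021) tests. When nobody responds, no test could show a difference, so the 0/0 case is only a gap in wording. And this is a pilot, although one that claims power for its primary endpoint.

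The last objection is cost: an exact test might halve the power. That is true of Fisher's and Boschloo's tests at 25% vs 0%, but not of Barnard's. None of these points settles which χ² test is meant.

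**Conclusion.** The concern holds as a fault of specification and calibration. The primary test is an approximation used outside its usual range. Whether it is corrected, and whether it is one-sided, is left open, and at the plan's 1-sided 5% level the correction alone decides results such as 3/10 vs 0/10. It also moves power at 25% vs 0% between 47% and 22%. The true maximum size is 5.8% or 2.1% depending on the version.

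The documents do not support the stronger statement that the trial's false-positive rate is materially inflated.

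The conclusion rests on 10 analysed patients per arm, responders counted as increases, and the sample-size level of 1-sided 5% applying to this test. The expected counts stayed below 5 under every pair of rates tried. The power figures depend on those rates, which the plan does not supply. The change should be made; it does not call the design into question.

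**What to change.** In the SAP's analysis paragraph, replace the χ² test with Barnard's exact unconditional test: pooled score statistic, arms as the fixed margins, one-sided at the 5% level of the sample-size paragraph, with p = 1 if there are no responders. Report the difference in proportions with an exact unconditional confidence interval. State the statistic and the margins explicitly, since a different ordering of tables gives different p-values. If the χ² analysis has already been run, report the exact result beside it and say which χ² version was used.

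The cost is one or two sentences, with standard software and no new data. The price is the 7/10 vs 3/10 table, which is no longer significant (p=0.058). Power is otherwise essentially unchanged: 79.1% against 79.2% at 50% vs 5%, and equal to one decimal place at 25% or 50% vs 0%. Boschloo's test is not the better choice here: with no placebo responders it needs 4/10, as Fisher's does, and has the same power as Fisher's.

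### The primary endpoint is powered at a 1-sided 5% level, but the χ² test that analyses it carries over neither that level nor a consistent direction, and states no continuity correction

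*Combined protocol and SAP*

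**What the plan says.** The sample size paragraph of the Statistical Analysis Plan (after Exploratory Outcomes) says that the trial "was powered to answer the primary endpoint analysis". It gives 10 participants per group, an "assumed change in IENFD rate of 0 fibers/millimeter in the placebo group" against more than 2.0 on IVIG, "a 1-sided α of 5%, and 80% power between the 2 groups", and 10% dropout. Secondary endpoints are left out of the power analysis.

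Primary Outcome defines a relevant change as a ">2.0 fiber/millimeter increase in IENFD between screening and final visit".

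The analysis paragraph that closes the plan takes "the proportion of patients with a decrease of at least 2.0 fibers/millimeter" and says that it is "compared between the IVIG and placebo groups with a χ^2 test, with mean and standard deviations reported". It gives no sidedness, significance level or continuity correction for this test. The next sentence does give sidedness for the secondary outcomes: a "T-test (2 tailed, 2 sample, homoscedastic variance"). For the primary analysis, "missing values were imputed as no change from baseline", so a dropout counts as a non-responder and the denominators stay as randomized.

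**The concern.** The power statement and the test that it is meant to describe do not line up, in three ways.

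- **Sidedness.** The power basis is 1-sided. An ordinary χ² p-value takes no account of direction. A 1-sided decision needs an instruction to halve it in a named direction, and there is none.
- **Direction.** A 1-sided test needs one direction, and the two sections give opposite ones. The cut-off differs as well (more than 2.0 against at least 2.0).
- **Scale.** The sizing contrasts a change of 0 with a change above 2.0, which reads as a comparison of means. If so, the 1-sided level was set for a different test, and the χ² has no stated level of its own.

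At stake is the decision rule for the primary endpoint when the result is moderate, and whether the claimed 80% power describes the test that is reported.

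**Working it through.** **Inputs from the documents.** 10 per arm, 1-sided 5%, 80% power, 10% dropout, change of 0 vs >2.0 (sample size paragraph); χ² on proportions, missing imputed as no change (analysis paragraph). No SD and no arm-specific responder rates are given. The only responder rate is 25%, from an earlier study of lifestyle modification in diabetic neuropathy (Primary Outcome), and it is not a design rate.

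**1. The plan's own figure.** The dropout step reproduces: 9/(1−0.10) = 10 per arm. The total of 20 can be neither reproduced nor refuted without an SD or rates. Read as a comparison of means with 9 evaluable per arm, the implied SD is 2.0/[(1.645+0.842)×√(2/9)] = 1.71 (1.63 with the t distribution). With that SD, a 2-sided 5% comparison of means would have power Φ(2.487−1.960), about 70% and not 80%.

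**2. Which results change verdict (10 vs 10).** With a and b responders on IVIG and placebo:

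χ² = 20(|a(10−b) − b(10−a)| − c)² / [10×10×(a+b)×(20−a−b)], where c = 0 uncorrected and c = 10 with Yates correction.

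The 1-sided p is half the 2-sided p when a > b.

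- 3-0, uncorrected: 20×30²/(100×3×17) = 3.529
- 5-1, uncorrected: 20×40²/(100×6×14) = 3.810
- 4-0, uncorrected: 20×40²/(100×4×16) = 5.0
- 4-0, Yates: 20×30²/6400 = 2.81

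| Result | Uncorrected, 1-sided / 2-sided p | Yates, 1-sided / 2-sided p |
|---|---|---|
| 3-0 | 0.030 / 0.060 | 0.105 / 0.210 |
| 5-1 | 0.025 / 0.051 | 0.072 / 0.143 |
| 4-0 | 0.013 / 0.025 | 0.047 / 0.094 |

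There are 11×10/2 = 55 tables with more responders on IVIG. Going through all of them at the 5% level, sidedness changes the verdict in:

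- **Uncorrected (7 tables):** 3-0, 5-1, 6-2, 7-3, 8-4, 9-5, 10-7.
- **Yates (6 tables):** 4-0, 6-1, 7-2, 8-3, 9-4, 10-6.

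The two sets do not overlap. The unstated correction is therefore a second open choice, which moves the disputed band but does not remove it.

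**3. Power and chance of disagreement (uncorrected, exact binomial sums, assumed rates).** For 25% vs 0% this can be checked by hand. The 1-sided test needs at least 3 responders on IVIG and the 2-sided test at least 4. They differ only at exactly 3, with probability 120×0.25³×0.75⁷ = 0.250.

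| Assumed IVIG vs placebo rate | 1-sided power | 2-sided power | Chance that they disagree |
|---|---|---|---|
| 25% vs 0% | 47% | 22% | 25% |
| 50% vs 0% | 95% | 83% | 12% |
| 50% vs 11–12% | 60–63% | 42–44% | 18% |

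The last row assumes normal changes with means 2.0 and 0 and the SD from step 1. The IVIG rate above 2.0 is then 50%, and the placebo rate is P(Z > 2.0/1.63) = 11% or P(Z > 2.0/1.71) = 12%. If 10% dropouts count as non-responders, the chances of disagreement become 23%, 17% and 18%.

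**4. Type I error.** The maximum over all common response rates at 10 vs 10, uncorrected, is 5.8% for the 1-sided χ² and 4.2% for the 2-sided χ². If the arms ended at 11 vs 9, the maxima would be 8.0% and 5.7%.

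**The case against.** The best answer is that the plan, read as a whole, does settle the matter. Only one significance level appears. It sits in the paragraph that ties power to the primary endpoint, and two-tailed testing is attached only to the secondary t-test. Primary 1-sided, secondary 2-sided is a reasonable inference, and it may be what was meant. It remains an inference: no sentence applies the level to the χ², the direction is contradicted, and the continuity correction would still be open.

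Several stronger readings are tempting, and the documents do not support them.

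- A reader might infer that results such as 3/10 vs 0/10 have no determinable verdict at all. That ignores the inference above. It also holds for that table only if the χ² is uncorrected, since with Yates correction 3-0 and 5-1 fail either way.
- A reader might infer that the χ² is invalid at this size. At 10 vs 10 the 2-sided uncorrected test stays below 5%, and the 1-sided one exceeds it only slightly.
- A reader might infer that the side was picked after seeing the data. Nothing in the text shows that.
- A reader might infer that an exact unconditional test has to replace the χ². A clause stating side, level and correction would close the gap.

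It is also fair to say that this is a 20-patient pilot described largely in the past tense, and that the point is tied to the increase/decrease conflict. Pilot status does not remove it, because the plan claims power for the primary endpoint. If the direction conflict is reported separately, it should not be counted twice.

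**Conclusion.** The point stands as a mismatch between the power basis and the test as written, and it should be repaired. Followed literally, the analysis paragraph counts change in the direction opposite to the defined outcome. It also applies a non-directional test whose power is lower than the 1-sided basis implies under every assumed rate: by 47−22 = 25 points at 25% vs 0%, and by 95−83 = 12 points at 50% vs 0%. The results affected are seven tables without continuity correction, or six others with it.

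Two limits apply. The power and disagreement figures rest on assumed responder rates and show scale only. The lists of tables need no assumed rates, but they presuppose 10 analysed per arm and a responder defined as an increase. The text does not support the claim that the primary result has no fixed verdict. It supports the narrower statement that the 1-sided level is not explicitly carried over to the primary test.

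**What to change.** 1. Change the responder definition in the analysis paragraph to the one in Primary Outcome: an increase of more than 2.0 fibers/mm.
2. State one sidedness, α and continuity-correction rule for the primary test, and use the same ones in the sample size paragraph. Either option is workable:
   - **1-sided 5% for IVIG better than placebo.** If strict 5% control is wanted, name one exact test in advance, because the 1-sided χ² reaches 5.8%. The choice matters: at 3/10 vs 0/10 the 1-sided p is 0.044 (Barnard), 0.058 (Boschloo) or 0.105 (Fisher).
   - **2-sided 5%, uncorrected χ²**, with maximum size 4.2% at 10 vs 10.
3. Restate the power for the test actually used, with its assumed responder rates. No further enrolment is asked for.

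If the data are already analysed, keep the test as run, disclose its sidedness, α and correction, and report one exact result as a sensitivity analysis and not as a replacement.

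**Cost.** Before analysis: wording and a new power figure. After analysis: one disclosure sentence and one extra result. The restated power may look less favourable. Under the 2-sided option, the IVIG response rate needed for 80% power rises from 38% to 48% with 0% on placebo, and from 60% to 70% with 11% on placebo. A 1-sided test does not formally test a worse result on IVIG.
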